Title of Study: Phase 1b Randomized, Double-Blind, Placebo-Controlled Study of the Safety of Therapeutic Treatment with Immunomodulatory Mesenchymal Stem Cells in Adults with COVID-19 Infection Requiring Mechanical Ventilation
Study Number: QUILT-COVID-19-MSC
Study Phase: Phase 1b

Study Objectives:Primary Objectives:

- To evaluate preliminary safety of BM-Allo.MSC vs placebo in terms of adverse events within 30 days of randomization.
- To evaluate preliminary efficacy of BM-Allo.MSC vs placebo in subjects who have tested positive for SARS-CoV-2 (COVID-19) and require ventilator support, as assessed by:
 - Mortality and cause of death within 30 days of randomization.
 - Number of ventilator-free days within 60 days of randomization.

Secondary Objectives:

- To further evaluate preliminary efficacy of BM-Allo.MSC vs placebo in subjects who have tested positive for SARS-CoV-2 (COVID-19), as assessed by:
 - Time from randomization to an improvement of one category in the 7-point ordinal scale.
 - Change in the 7-point ordinal scale from baseline.
 - Change in National Early Warning Score (NEWS) from baseline.
 - Time from randomization to discharge or to a NEWS of ≤ 2 maintained for 24 hours, whichever occurs first.
 - Change from baseline in Sequential Organ Failure Assessment (SOFA) score on days 8, 15, 22, and 29.
 - Number of days requiring oxygen within 60 days of randomization.
 - Duration of hospitalization from randomization.
- To further evaluate the safety of BM-Allo.MSC in subjects who have tested positive for SARS-CoV-2 (COVID-19), as assessed by:
 - Incidence of SAEs within 30 days of randomization.
 - Change from baseline in hemoglobin.
 - Change from baseline in platelets.
 - Change from baseline in white blood cell count.
 - Change from baseline in vital signs.

Study Design:

This is a phase 1b randomized, double-blind, placebo-controlled study in adult subjects with Coronavirus Disease 2019 (COVID-19). This clinical trial will evaluate the preliminary safety and efficacy of BM-Allo.MSC vs placebo in treating subjects with severe disease requiring ventilator support during COVID-19 infection. Only subjects with moderate or severe ARDS (per Berlin criteria; see [Appendix 1](#)) will be enrolled in this study.

COVID-19 infection causes progressive severe lung infection that can lead to death in a significant number of infected patients. Prior work using allogeneic mesenchymal stem cells (MSCs) in severely infected individuals has shown promise in reversing the severe consequences of infection in critically ill patients. Thus, the potential exists for allogeneic MSCs to slow or halt disease progression and reduce time on ventilators in critically ill patients infected with COVID-19, and thus improve disease outcomes.

A total of 45 subjects receiving care in the critical care or ICU setting with mechanical ventilation for COVID-19 will be enrolled in this study. Subjects will be randomized 2:1 to the experimental arm (30 subjects) and control arm (15 subjects).

Subjects in the experimental arm will be administered BM-Allo.MSC ($0.7\text{-}1.3 \times 10^6$ cells/kg IV) on day 1 followed by day 5 (± 1 day), if subject still requires ventilation on day 5. Subjects will be followed through day 60. Subjects in the control arm will be administered placebo on a schedule identical to that of the experimental arm and followed through day 60.

BM-Allo.MSC and placebo may be provided to the clinical treatment site as a cryopreserved preparation. The cryopreserved product will contain BM-Allo.MSC in 5% albumin (human), USP, and CryoStor 10 (CS10) (in 1:1 ratio) in a volume of 100 mL. The placebo will consist of 5% albumin (human), USP, and CS10 (1:1 ratio) in a volume of 100 mL.

All subjects will be assessed using a 7-point ordinal scale that evaluates clinical status at the first assessment of each study day. The scale is as follows: 1) death; 2) hospitalized, on invasive mechanical ventilation or extracorporeal membrane oxygenation (ECMO); 3) hospitalized, on non-invasive ventilation or high-flow oxygen devices; 4) hospitalized, requiring supplemental oxygen; 5) hospitalized, not requiring supplemental oxygen; 6) not hospitalized, limitation on activities; 7) not hospitalized, no limitations on activities.

In addition, all subjects will be assessed using the standard National Early Warning Score (NEWS) score ([Royal College of Physicians 2012](#)). The NEWS score has demonstrated an ability to identify patients at risk of poor outcomes and will be used as a measure of efficacy. This score is based on 7 clinical parameters (respiration rate, oxygen saturation, any supplemental oxygen, temperature, systolic blood pressure, heart rate, level of consciousness).

Safety will be assessed for all subjects and will include monitoring of vital signs and incidence and severity of adverse events. Blood samples will be collected for hematology and chemistry analyses.

Safety will be monitored throughout the study. After the first 5 subjects are randomized (giving at least 3 subjects in the experimental arm) enrollment will be paused and the NantKwest Safety Review Committee (SRC) will perform an evaluation of safety once the 5 subjects have completed the 14 day toxicity assessment period. Enrollment will continue if the safety evaluation from the initial 5 subjects suggests that the therapy is safe.

Primary Endpoints:

- Incidence of AEs within 30 days of randomization.
- Mortality within 30 days of randomization.
- Cause of death within 30 days of randomization
- Number of ventilator-free days within 60 days of randomization.

Secondary Endpoints:

- Time from randomization to an improvement of one category using the ordinal scale.
- Change in the 7-point ordinal scale from baseline.
- Change in NEWS from baseline.
- Time from randomization to discharge or to a NEWS of ≤ 2 maintained for 24 hours, whichever occurs first.
- Change from baseline in Sequential Organ Failure Assessment (SOFA) score on days 8, 15, 22, and 29.
- Number of days requiring oxygen.
- Duration of hospitalization from randomization.
- Incidence of SAEs within 30 days of randomization
- Change from baseline in hemoglobin, platelets, and white blood cell (WBC) count.
- Changes in vital signs from baseline.

Enrollment (planned):

A total of 45 subjects receiving care in the critical care or ICU setting with mechanical ventilation for COVID-19 will be randomized 2:1 to the experimental arm (30 subjects) and control arm (15 subjects) in this study.

Eligibility Criteria:***Inclusion Criteria:***

1. Age ≥ 18 years old.
2. Able to understand and provide a signed informed consent that fulfills the relevant Institutional Review Board (IRB) or Independent Ethics Committee (IEC) guidelines. For subjects that are intubated and/or sedated, or otherwise unable to provide consent, prospective consent from a legally-authorized representative is required. The subject or his/her legally authorized representative must be able to provide consent.
3. Has laboratory-confirmed positive novel coronavirus (SARS-CoV-2) test, as determined by polymerase chain reaction (PCR), or other commercial or public health assay in any specimen < 72 hours prior to enrollment, or meets the criteria to guide the evaluation and testing of patients under investigation (PUI) for COVID-19 (<https://emergency.cdc.gov/han/2020/HAN00428.asp>).

4. Requiring mechanical ventilatory support with moderate to severe Acute Respiratory Distress Syndrome (ARDS) as determined by the Berlin criteria:
 - a. Bilateral opacities present on a chest radiograph or computed tomographic (CT) scan. These opacities are not fully explained by pleural effusions, lobar collapse, lung collapse, or pulmonary nodules.
 - b. Origin of Edema: Respiratory failure not fully explained by cardiac failure or fluid overload.
 - c. Oxygenation: Moderate to severe impairment of oxygenation must be present, as defined by the ratio of arterial oxygen tension to fraction of inspired oxygen ($\text{PaO}_2/\text{FiO}_2$). The severity of the hypoxemia defines the severity of the ARDS:
 - Moderate: $\text{PaO}_2/\text{FiO}_2 > 100 \text{ mmHg}$ and $\leq 200 \text{ mmHg}$, on ventilator settings that include $\text{PEEP} \geq 5 \text{ cm H}_2\text{O}$
 - Severe: $\text{PaO}_2/\text{FiO}_2 \leq 100 \text{ mmHg}$ on ventilator settings that include $\text{PEEP} \geq 5 \text{ cm H}_2\text{O}$
- Subjects receiving extracorporeal membrane oxygenation (ECMO) will not be enrolled in this study.
5. High-sensitivity C-reactive Protein (hs-CRP) serum level $> 4.0 \text{ mg/dL}$
6. Acute Physiology and Chronic Health Evaluation (APACHE IV) score > 5
7. Agrees to the collection of nasopharyngeal (NP) swabs and venous blood per protocol.
8. Ability to attend required study visits and return for adequate follow-up, as required by this protocol.
9. Agreement to practice effective contraception for female subjects of child-bearing potential and non-sterile males. Female subjects of child-bearing potential must agree to use effective contraception while on study and for at least 1 month after the last dose of BM-Allo.MSC. Non-sterile male subjects must agree to use a condom while on study and for up to 1 month after the dose of BM-Allo.MSC. Effective contraception includes surgical sterilization (eg, vasectomy, tubal ligation), two forms of barrier methods (eg, condom, diaphragm) used with spermicide, intrauterine devices (IUDs), oral contraceptives, and abstinence.

Exclusion Criteria:

1. Known hypersensitivity to any component of the study medication(s), including dimethyl sulfoxide (DMSO).
2. Signs of multisystem organ failure. Liver function tests (LFTs) $> 5x$ normal.
3. Intubated > 72 continuous hours.
4. Assessed by the Investigator to be unable or unwilling to comply with the requirements of the protocol.
5. Pregnant and nursing women. A negative serum pregnancy test during screening (within 72 hours prior to the first dose) must be documented before MSCs are administered to a female subject of child-bearing potential.

Products, Dosage, and Mode of Administration:		
Investigational Products	Dosage	Mode of Administration
BM-Allo.MSC	$0.7\text{-}1.3 \times 10^6$ cells/kg	IV
Duration of Treatment:		
Subjects in the experimental arm will be administered BM-Allo.MSC ($0.7\text{-}1.3 \times 10^6$ cells/kg IV) on day 1 followed by day 5 (± 1 day), if subject still requires ventilation on day 5. Subjects will be followed through day 60. Subjects in the control arm will be treated with placebo on a schedule identical to that of the experimental arm and followed through day 60.		
Duration of Follow-up:		
Subjects who receive study treatment for any reason will be followed via regular visits with a health care professional until either death (by any cause) or for a minimum of 30 days after administration of BM-Allo.MSC.		
Reference Therapy, Dosage, and Mode of Administration:		
Subjects randomized to the control arm will receive an IV infusion of placebo, provided to the clinical treatment site as a cryopreserved preparation. The cryopreserved placebo consists of 5% albumin (human), USP, and CryoStor 10 (1:1 ratio) in a volume of 100 mL.		

Evaluation of Endpoints:

Safety: Safety endpoints include assessments of treatment-emergent AEs, SAEs, and changes in hemoglobin, platelets, and white blood cell (WBC) count safety laboratory tests and vital signs. Toxicities will be graded using CTCAE Version 5.0

Efficacy: Mortality and cause of death within 30 days of randomization, number of ventilator-free days within 60 days of randomization, number of subjects reporting each severity rating on the 7-point ordinal scale, and number of subjects with improved NEWS scores and 7-point ordinal scale.

Statistical Methods:

All subjects receiving at least one dose of study drug (ie, the Safety population) will be included in the safety and efficacy analyses. Statistical analysis will be descriptive and presented by treatment arm. No statistical testing will be performed.

Safety Analyses:

Overall safety will be assessed by descriptive analyses using tabulated frequencies of AEs by grade using CTCAE version 5 in terms of treatment-emergent AEs, SAEs, and AEs by grade and clinically significant changes in safety laboratory tests and vital signs.

Efficacy Analyses:

The mortality rate within 30 days of randomization and 95% confidence interval will be summarized. Cause of death will be summarized. The mean number of ventilator-free days and number of days requiring oxygen within 60 days of randomization and the mean duration of hospitalization will be summarized.

Time from randomization to an improvement of one category on the 7-point ordinal scale will be summarized. The mean change from baseline on the 7-point ordinal scale at each post-baseline evaluation time point will be summarized.

The mean change from baseline for each parameter of NEWS and the overall score at each post-baseline evaluation time point will be summarized. Time from randomization to discharge or to a NEWS of ≤ 2 maintained for 24 hours, whichever occurs first will be summarized. The mean change from baseline in SOFA score at each post-baseline evaluation time point will be summarized.

Figure 1: Study Treatment Schema

[figure not shown]

Table 5: Schedule of Events

	Baseline/Screening ^a	Study Day						
		1	5	8	15	22	29	60/EOS
Study Day	-1 or 1	± 1						± 4
General Assessments								
Informed consent	X							
Inclusion/exclusion	X							
Demographics	X							
Medical history	X							
Confirm contraceptive measures	X							
APACHE assessment	X							
High-sensitivity CRP	X							
Physical exam: height, weight ^b	X	X	X					
Vital signs ^c	X	Daily, throughout study period						
SOFA assessment	X	X		X	X	X	X	X
Ordinal scale (7-point)	X	X		X	X	X	X	X
NEWS ^c	X	Daily, throughout study period						X
Concomitant medications ^c	X	Daily, throughout study period						X
Adverse event collection ^c	X	Daily, throughout study period						X

	Baseline/Screening ^a	Study Day						
Study Day	-1 or 1	1	5	8	15	22	29	60/EOS
Windows (days)		± 1						± 4
Study drug administration								
BM-Allo.MSC or Placebo		X	X ^d					
Laboratory Assessments								
Collect NP swabs	X	X						
Chemistry panel ^e	X	X		X	X	X	X	X
Hematology ^f	X	X		X	X	X	X	X
Collect whole blood for immunogenicity and cytokine analyses	X	X		X	X	X	X	X
Pregnancy test ^g	X	X						

^a Baseline/screening assessments may be done ≤ 1 calendar day prior to the first dose of BM-Allo.MSC or placebo. Day 1 assessments do not need to be repeated if baseline/screening is done on study day 1. Assessments performed on day 1 must be performed before dosing.

^b Height required at baseline/screening visit only. Weight on day 1 should be used to calculate drug dose.

^c Vital signs, concomitant medications, NEWS assessment, and adverse event collection will occur daily throughout the study period (ie, each day beginning day 1 and continuing through day 29). Vital signs of temperature, heart rate, blood pressure, oxygen saturation, and respiratory rate will be assessed at every visit.

^d Dose to be administered on day 1 followed by day 5 (± 1 day), if subject still requires ventilation on day 5.

^e See [Table 4](#) for additional details on laboratory assessments. Blood draws for lab assessments should occur prior to BM-Allo.MSC or placebo administration.

^f Hematology to include CBC with differential (5 part) as outlined in Table 4. Blood draws for lab assessments should occur prior to BM-Allo.MSC or placebo administration.

[figure not shown]
^g Serum pregnancy tests for females of child-bearing potential.

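### The secondary endpoint of discharge or NEWS ≤ 2 for 24 hours does not require the subject to be off mechanical ventilation

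*Combined protocol and SAP*

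**What the plan says.** References are to the current synopsis, that is, the double-blind version with the cryopreserved product.

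- **Endpoint.** The Secondary Objectives and Secondary Endpoints both contain "Time from randomization to discharge or to a NEWS of ≤ 2 maintained for 24 hours, whichever occurs first". Under Efficacy Analyses the plan says only: "Time from randomization to discharge or to a NEWS of ≤ 2 maintained for 24 hours, whichever occurs first will be summarized". None of the three places mentions ventilation status.
- **Score.** Study Design states that "all subjects will be assessed using the standard National Early Warning Score (NEWS) score" and that it "will be used as a measure of efficacy". Seven parameters are listed: respiration rate, oxygen saturation, and "any supplemental oxygen, temperature, systolic blood pressure, heart rate, level of consciousness". There are no point weights, and there is no rule for a ventilated or sedated subject.
- **Population.** Inclusion criterion 4 reads: "Requiring mechanical ventilatory support with moderate to severe Acute Respiratory Distress Syndrome (ARDS) as determined by the Berlin criteria". Inclusion criterion 2 expects some to be sedated: "For subjects that are intubated and/or sedated, or otherwise unable to provide consent".
- **Timing.** Table 5, footnote c, has NEWS assessed every day from day 1 to day 29, so it is scored while subjects are ventilated.
- **Other measures of ventilation.** Category 2 of the 7-point ordinal scale is invasive ventilation or ECMO in hospital. Ventilator-free days within 60 days is a primary endpoint.

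**The concern.** Every subject starts on a ventilator, so an endpoint that dates improvement should say whether being off the ventilator is part of it. This one does not. Respiratory support enters NEWS directly only through the yes/no oxygen item, which treats a ventilator and a nasal cannula alike. Two further items, respiration rate and saturation, can be held near normal by the ventilator itself.

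A subject could therefore be dated as an event while still in ordinal category 2. Two subjects with the same lungs could also be classified differently because one is sedated and the other awake. No statistical testing is planned, so the descriptive summary of this endpoint is itself the result that readers will see, and its meaning should be clear.

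**Working it through.** The plan gives no figure for this endpoint, so there is none to reproduce. The check has two parts.

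**1. Does the text bar a ventilated subject from being an event?** Set side by side: the endpoint carries no ventilation condition; the parameter list has no ventilation item; all subjects enter ventilated; NEWS is scored daily from day 1. Nothing in these places prevents it.

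**2. Can the score fall to 2 or below on a ventilator?** This depends on weights that the documents do not give.

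Inputs:
- Threshold: 2 (Secondary Endpoints).
- Points for supplemental oxygen, *w_O*: assumed 0 to 3.
- Points for reduced consciousness, *w_C*: assumed 0 to 3.
- The other five items: set to 0, the case most favourable to meeting the threshold.

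Formula: NEWS = *w_O* + *w_C* + (sum of the other five items).

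Awake ventilated subject (*w_C* = 0, so NEWS = *w_O*):

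| *w_O* | NEWS | ≤ 2? | Points left for all other items (2 − *w_O*) |
|---|---|---|---|
| 0 | 0 | yes | 2 |
| 1 | 1 | yes | 1 |
| 2 | 2 | yes | 0 |
| 3 | 3 | no | none |

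At *w_O* = 2 the criterion is met only if all six other items stay at 0 for 24 hours.

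Sedated ventilated subject (NEWS = *w_O* + *w_C*): the threshold is met for 6 of the 4 × 4 = 16 weight pairs, namely (0,0), (0,1), (0,2), (1,0), (1,1) and (2,0). If both items score at least 1, it is met for 1 of 3 × 3 = 9 pairs, namely (1,1). These are counts of assumed weights, not probabilities.

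Example: with *w_O* = 2 and *w_C* = 3, the awake subject scores 2 + 0 = 2 and is an event. The sedated subject scores 2 + 3 = 5 and is not.

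**Scale.** The planned arms are 30 and 15. One such subject is 1/30 = 3.3% of the experimental arm or 1/15 = 6.7% of the control arm.

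**The case against.** The strongest reply is that the problem may never occur. Whether a ventilated subject can reach the threshold rests on weights found only in a cited source. Even at 2 points for oxygen, the subject must be awake and normal on every other item for 24 hours, in a population with moderate or severe ARDS. This stands. It makes the route narrow and its frequency unknown, but it does not supply the missing condition.

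Three stronger inferences are tempting, and the documents do not support them:

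- *Ventilated subjects are scored as recovered.* The plan never calls this endpoint recovery; it calls NEWS a measure of efficacy.
- *The endpoint contradicts the primary measure.* A physiological score and ventilator-free days measure different things. They may disagree for one subject without contradiction, and ventilator-free days and the ordinal scale would still record that subject as ventilated.
- *A transfer out on a ventilator counts as discharge.* The synopsis neither defines discharge nor mentions transfers, and the ordinal scale places ventilated subjects only among the hospitalized. The most that can be said is that the term is undefined.

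It is also fair to say that this is one of ten secondary endpoints in a double-blind phase 1b study, with the same rule in both arms and no stated decision resting on it. That limits the consequences. Finally, the text available consists of synopses and schedules. If a fuller endpoint definition or NEWS scoring rule stands elsewhere, it may answer the point; nothing in the synopsis or Table 5 does.

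**Conclusion.** The gap in the definition is established from the text alone: the endpoint does not require the subject to be off mechanical ventilation, and no listed NEWS parameter supplies that condition. That a ventilated subject can actually meet it is conditional on an oxygen item of 2 points or less and all other items within the remaining allowance for 24 hours. At 3 points the NEWS route closes. It applies mainly to awake subjects.

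A reader might take 3.3% and 6.7% as the distortion in the result. They are only the share of an arm that one subject represents. A subject who meets the criterion while ventilated may well meet it again after extubation, so the error may lie in the date of the event and not in its occurrence. The shift in the time summary cannot be calculated from the documents.

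This is a worthwhile, inexpensive improvement to a descriptive secondary endpoint. The primary endpoints are unaffected.

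**What to change.** Reword the endpoint identically under Secondary Objectives, Secondary Endpoints and Efficacy Analyses, for example: time from randomization to the first of (a) discharge alive, not on invasive mechanical ventilation, or (b) NEWS of 2 or less held for 24 hours while receiving neither invasive mechanical ventilation nor ECMO.

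This follows the boundary the plan already draws at ordinal category 2. Subjects on non-invasive ventilation or high-flow oxygen (category 3) could still qualify. If the sponsor wants the line elsewhere, the same sentence can say so.

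The cost is one sentence in three places. Ventilation status is already needed for ventilator-free days and the ordinal scale, so no new data are required. Table 5 schedules the ordinal scale only at visits, so the record behind ventilator-free days is the better source for the 24-hour condition. The downside is slightly fewer or later events.

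### Mean hospital stay has no time window and no rule for subjects still in hospital at day 60 or dying in hospital, so it is not well defined and can distort the comparison of arms in either direction

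*Combined protocol and SAP*

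**What the plan says.** All references are to the third and latest synopsis in the combined protocol and SAP.

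- **Secondary Objectives and Secondary Endpoints** define the measure as "Duration of hospitalization from randomization". This fixes a start and no end.
- **Statistical Methods, Efficacy Analyses** asks for its mean: "number of days requiring oxygen within 60 days of randomization and the mean duration of hospitalization will be summarized".
- **Neighbouring endpoints** carry a window. The primary endpoint is "Number of ventilator-free days within 60 days of randomization", and the objective listed just before hospital stay is "Number of days requiring oxygen within 60 days of randomization".
- **Follow-up**: Study Design states "Subjects will be followed through day 60", and the schedule of events places the last visit at day 60 with a window of ±4 days. Duration of Follow-up says subjects are followed "until either death (by any cause) or for a minimum of 30 days after administration of BM-Allo.MSC", which does not extend hospital follow-up past day 60.
- **Analysis set**: "All subjects receiving at least one dose of study drug (ie, the Safety population) will be included in the safety and efficacy analyses". The analysis is descriptive by arm, without testing.

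The supplied text does not say whether a stay in progress at day 60 is dropped, censored or counted to day 60. Nor does it say how a stay ended by death is valued.

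**The concern.** A mean needs a finished value for every subject. Here two groups lack one: survivors still in hospital when observation stops, and subjects whose stay ended because they died. All subjects enter ventilated with moderate or severe ARDS, so both groups are plausible, although the documents give no rate for either.

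Without a rule, the choice would be made after the data are seen, and the candidate choices answer different questions. Because nothing is tested, the by-arm summary is itself the result that readers will compare. With 30 and 15 subjects, the handling of a few long stays or early deaths can move that comparison by several days.

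**Working it through.** **No design figure to reproduce.** The documents state no expected stay, spread, death rate or effect. The only arithmetic available is the allocation: 45 × 2/3 = 30 and 45 × 1/3 = 15, which agrees. Everything below rests on assumed inputs. Differences are control minus BM-Allo.MSC.

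**Step 1: survivors only.** Assume lognormal stays with median m and log-SD s. Let z = (ln 60 − ln m)/s.

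- Share discharged by day 60: F = Φ(z)
- Full mean: M = m·exp(s²/2)
- Part of the mean from stays up to 60 days: A = M·Φ(z − s)
- Mean with unfinished stays dropped: A/F
- Mean with stays counted to day 60: A + 60(1 − F)

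Central case: control median 35, BM-Allo.MSC median 0.75 × 35 = 26.25, s = 0.7 in both arms.

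| | Control | BM-Allo.MSC | Difference |
|---|---|---|---|
| z | 0.770 | 1.181 | |
| Still in hospital, 1 − F | 22.1% | 11.9% | |
| A | 23.61 | 22.96 | |
| Dropped, A/F | 30.29 | 26.06 | 4.23 |
| Counted to day 60 | 36.85 | 30.09 | 6.75 |
| Full stay, M | 44.72 | 33.54 | 11.18 |

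Relative to counting to day 60, dropping loses 1 − 4.23/6.75 = 37% of the difference. Over control medians of 25-45 and log-SDs of 0.5-0.9, always with stays 25% shorter on BM-Allo.MSC, 4-38% of control and 1-26% of BM-Allo.MSC survivors remain in hospital. The difference is 3.1-5.8 days dropped against 5.5-8.1 counted to day 60, a loss of 14-45%.

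**Step 2: is the direction fixed?** For each arm's mean, yes: every dropped stay exceeds 60 days and every retained one does not, so the retained mean lies below both alternatives. For the arm difference, no.

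- *Unequal spreads.* Control median 35, s = 0.3; BM-Allo.MSC median 30, s = 0.9. Then 4% and 22% remain in hospital. Dropping gives 35.4 − 25.9 = 9.6 (from unrounded means), counting to day 60 gives 36.3 − 33.4 = 2.9, and the full stay gives 36.6 − 45.0 = −8.4. Both handlings overstate the full-stay difference here, whereas both understate it in the table above.
- *Exact counts.* Take 15 and 30 subjects with discharged means of 30 and 25 days. Dropping always gives 5.0. With 3 and 3 still in hospital, counting to day 60 gives (12×30 + 3×60)/15 − (27×25 + 3×60)/30 = 36.0 − 28.5 = 7.5. With 1 and 6 it gives (14×30 + 60)/15 − (24×25 + 6×60)/30 = 32.0 − 32.0 = 0.0.

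**Step 3: deaths.** Keep the central case, count to day 60, and assume that 50% of control and 30% of BM-Allo.MSC subjects die in hospital, uniformly over days 1-30 (mean 15.5).

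- Control: 0.5×36.85 + 0.5×15.5 = 26.17
- BM-Allo.MSC: 0.7×30.09 + 0.3×15.5 = 25.71
- Difference: about 0.5 days, against 6.75 among survivors

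Now give both arms the same survivor mean of 36.85, with deaths of 50% and 20%. The means are 26.17 and 0.8×36.85 + 0.2×15.5 = 32.58, a difference of −6.4 days. The arm with fewer deaths appears to stay longer in hospital.

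**Step 4: the alternative measures on the first death scenario.**

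- Discharged alive by day 60: 0.5×(1 − 0.221) = 39% against 0.7×(1 − 0.119) = 62%
- Mean days alive and out of hospital: 0.5×(60 − 36.85) = 11.6 against 0.7×(60 − 30.09) = 20.9

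Neither measure credits an early death as a good outcome.

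**The case against.** The best defence is that this is loose drafting. The Secondary Endpoints list also omits the window for oxygen days, although the objectives and the analysis text supply one. All dosed subjects are in the efficacy analyses, which argues against an analysis of completed stays only; with observation ending at day 60, counting to day 60 is at least as natural. That stands. A reader might infer that day-60 inpatients have no value and leave the mean, but the documents never say so.

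A reader might also infer that the plan will understate the difference between arms. That does not follow: the 14-45% loss assumes that unfinished stays are dropped, that BM-Allo.MSC shortens stays, and that the spread is equal in both arms.

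Three further points carry weight. The ordinal scale is scheduled at the day-60 visit and separates inpatients from outpatients, so the number still in hospital is nearly available by arm already. The endpoint is secondary and untested. And in the Step 1 settings the gap between the two handlings is 1.0-2.9 days, against a standard error of 3.9-6.0 days for the difference counted to day 60, even if all 45 survive.

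What remains is that membership of the analysis set does not say what number an unfinished stay receives, and no reading of the text resolves deaths. The supplied text consists of synopses and schedules, so a rule in the full protocol body cannot be excluded.

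**Conclusion.** The point holds as a gap in definition. A plain mean is not a valid summary of a duration that is cut off at day 60 and can be ended early by death. If unfinished stays are dropped, each arm's mean is too low. If they are counted to day 60, the result is a restricted quantity that the plan does not name, and early deaths pass as short stays. Under either handling the arm difference may be too small, too large or reversed; the documents do not support a claim that it is always understated.

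No size can be derived from the documents. The illustrations depend on assumed lognormal stays and assumed deaths. The consequence is modest: one secondary, descriptive endpoint among several in a 45-subject phase 1b trial. The remedy is cheap enough to justify making it before the data are summarized.

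**What to change.** In Secondary Objectives, Secondary Endpoints and Efficacy Analyses of the latest synopsis:

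1. Limit the hospital-stay endpoint to 60 days from randomization.
2. Make the main by-arm summary the cumulative incidence of discharge alive by day 60, with death as a competing event and living inpatients censored at day 60.
3. If a mean is wanted, report days alive and out of hospital through day 60. Deaths contribute no days after death, and inpatients contribute none while in hospital.
4. Beside it, report by arm the number still in hospital at day 60 and the number who died in hospital.
5. Take status at day 60 itself, since the last visit may fall up to four days either side.

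The cost is a wording change and a few table lines, using discharge and death dates that the existing endpoints already need. If days after readmission are to be subtracted, readmission dates must be recorded as well. The drawback is that the result describes the first 60 days and not total length of stay, which follow-up to day 60 cannot deliver in any case.
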